Study Design, Population, Apparatus and Investigational Plan

Aims 1 & 2.

Design: This is prospective, experimental design includes a block randomized, blinded, sham controlled, mixed effects model with sequential assignment to two treatment arms (1 or 10 Hz rTMS) and random assignment to three experimental conditions within each arm (Table 1).

Randomization: Subjects will be assigned sequentially to one of two parallel groups (1 Hz or 10 Hz rTMS: Table 1.5). Next, they will complete three experimental test sessions (Table 1). The order of test sessions is randomized. A minimum two week washout period will follow each session to minimize session to session carry forward effects.¹⁵ Washout can exceed two weeks.

[figure not shown]

Figure 1.5. Subject flow.

Study visits: Study visits will be to the transcranial magnetic stimulation laboratory, room 654-2, located on the 6th floor of the Biomedical II research building on the UAMS

Study Title: Regulating homeostatic plasticity and the physiological response to rTMS
 PI: [name]
 Institution: University of Arkansas for Medical Sciences
 Support: Department of Neurobiology and Dev. Scs.

campus. In total, there will be 4 study visits - 1 consent/screening visit and 3 laboratory visits per subject. The 3 laboratory study visits will be separated in time by a minimum of two weeks. The time required to complete a study visit ranges from 1 hour, when TMS/EEG is not collected, to 3.5 hours, when TMS/EEG is collected. TMS/EEG is recorded immediately before and after tDCS preconditioning, immediately following rTMS and after a 20-30-minute delay to examine the acute and lasting effects.

Subject flow: Twenty healthy subjects who meet the entry criteria and pass safety screening for tDCS and TMS will be enrolled (Figure 1.5). Ten subjects will be tested in each aim, with two parallel groups of 5 subjects receiving either 1 or 10 Hz rTMS. Two randomization lists of 10, each balanced between tDCS over TC and tDCS over DLFC, were generated based

on uniformly distributed random number generation in SAS v9.4. The first 10 recruited subjects will receive 1Hz rTMS treatment while the second 10 will receive

Experimental conditions & TMS/EEG assessments.								
Condition†	TMS/EEG	tDCS	TMS/EEG	rTMS	TMS/EEG	30 min delay	TMS/EEG	
1		sham		sham				
2		sham		active				
3		active		active				
Time (mins)	0	20	40	60	80	100	130	

Table 1. † The order of conditions is randomized. A 2 week washout separates each condition.

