Data collection will be accomplished via case report forms and electronic recording via the devices used in this study. The Principal Investigator will carefully monitor study procedures to protect the safety of research subjects, the quality of the data and the integrity of the study. Participant's data will be de-identified using codes, personal identifiers will be kept separate from study data, and data will be locked in file cabinets or drawers in the TMS laboratory and in the PI's office, if hardcopy, or on a password-protected UAMS server, both located behind locked doors in a restricted access area of the UAMS campus. Only authorized individuals will have access to the code and information that identifies the subjects in this study. Following informed consent to participate, patient's hospital and outpatient records may be reviewed to identify appropriate candidates for the study. Any data obtained as part of the patient's clinical care may be reviewed to determine whether the subject meets inclusion and does not meet exclusion criteria.

Data Analysis

Analyses and Power calculations.

Aims 1 & 2 examine the effect of treatment dose on one primary outcome measure – a difference score between sham and active rTMS in the LMFP of TEPs (Δ LMFP) recorded from TC and DLFC. The analysis plan is the same for both aims. Hierarchical Linear Models (HLMs) will be used due to the nested structure of the design. HLMs will fit the complex covariance structure of the dosing schedule – sham and active tDCS nested within rTMS treatment frequency (1 Hz and 10 Hz). Four primary responses will be estimated, namely Δ LMFP for the sham vs active tDCS and the 1 Hz vs 10 Hz rTMS conditions. From these four responses, four contrasts of interest will be estimated: (1) sham vs active tDCS for 1 Hz rTMS, (2) sham vs active tDCS for 10 Hz rTMS, (3) 1 Hz vs 10 Hz rTMS for sham tDCS, and (4) 1 Hz vs 10 Hz rTMS for active tDCS. An additional 6 contrasts will be used to examine differences in the means for the rTMS post 1 (acute) and post 2 (lasting) time periods. The HLM methodology will estimate the means and standard errors for all these contrasts of interest with a Bonferroni comparison procedure to adjust for the multiple contrasts.

Power Estimates

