One purpose of the pilot study is to collect TEP data for a power analysis because such data does not currently exist. To estimate power for the pilot study, effect sizes for the contrasts of interest in Aims 1 and 2 were estimated from the means and SDs of MEP amplitudes in two published studies that used anodal, 1 mA tDCS to precondition the motor cortex before rTMS was delivered a 1 Hz²⁸ or 5 Hz³ (power estimates for 10 Hz stimulation were based on the 5 Hz study). As in our design, change in cortical

Study Title: Regulating homeostatic plasticity and the physiological response to rTMS
PI: [name]
Institution: University of Arkansas for Medical Sciences
Support: Department of Neurobiology and Dev. Scs.

excitability was measured both immediately following rTMS (acute) and 30 minutes later (lasting effects). PASS 12 was used to calculate power by estimating power, conservatively, as two-sample t-tests (n=5 for all comparisons). For 1 Hz TMS, the power to detect a difference in MEP amplitude between the sham (mean=.89, SD=.08) and active (.64; .08) tDCS conditions was 99% acutely (effect size=2.95) and 48% at 30 minutes (effect size=95%). For the 5 Hz condition, power to detect a difference in MEP amplitude between sham (.99; .16) and active (.98; .16) tDCS was only 6% acutely (effect size=.06) but 100% at 30 minutes (effect size=4.80). Finally, the power to detect a difference in MEP amplitude between 1Hz (.64; .08) and 10Hz (.98; .16) rTMS (after active tDCS preconditioning) was 94% acutely (effect size=2.68) but only 8% at 30 minutes (effect size=.39). Importantly, anodal preconditioning induced LTD (a decrease in the MEP amplitude) in both the 1 and 5 Hz conditions but, consistent with the hypothesis for Aims 1 & 2, the effect was stronger for 1 Hz than 5 Hz rTMS. These estimates give confidence that the sample sizes of our pilot study are sufficient to test Aims 1 & 2.

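### The 94% power for 1 Hz versus 10 Hz rTMS is for single-condition amplitudes, not the planned difference score, and calling it conservative is not justified for that between-group contrast

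*Combined protocol and SAP*

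**What the plan says.** Under Analyses and Power calculations, the primary outcome for Aims 1 and 2 is "a difference score between sham and active rTMS in the LMFP of TEPs". Four contrasts follow. Contrasts 1 and 2 compare sham with active tDCS within a frequency. Contrasts 3 and 4 compare the two frequencies, and contrast 4 is "1 Hz vs 10 Hz rTMS for active tDCS". All contrasts are to be estimated by hierarchical linear models with a Bonferroni adjustment. The design section places the frequencies in separate subjects, "with two parallel groups of 5 subjects receiving either 1 or 10 Hz rTMS" within each aim.

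Under Power Estimates, the protocol says that "PASS 12 was used to calculate power by estimating power, conservatively, as two-sample t-tests (n=5 for all comparisons"). For contrast 4 it reports "the power to detect a difference in MEP amplitude between 1Hz (.64; .08) and 10Hz (.98; .16) rTMS (after active tDCS preconditioning") and gives the result as "was 94% acutely (effect size=2.68) but only 8% at 30 minutes (effect size=.39"). The section ends by concluding that the pilot's sample sizes are adequate for Aims 1 and 2. It gives no SD for the difference score, no correlation between a subject's sessions, and no alpha.

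**The concern.** The power calculation and the planned analysis use different quantities. The first compares the amplitude after active tDCS plus rTMS in two groups. The second subtracts each subject's sham-rTMS value first.

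In contrasts 1 and 2 the subtraction makes no difference, because both terms share the same sham/sham session and it cancels: (A − S) − (B − S) = A − B. What remains is a within-subject comparison, and treating it as unpaired can be conservative. In contrasts 3 and 4 each frequency group subtracts its own sham session, so that variance stays in, and there is no pairing for an unpaired test to ignore.

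The 94% is the only high power printed for a frequency comparison, and it supports the statement that the sample is sufficient. The working hypothesis includes a stronger effect at 1 Hz than at 10 Hz. A reader who takes 94% as a floor could read too much into a null frequency result.

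**Working it through.** **Inputs.** From Power Estimates: means 0.64 and 0.98, SDs 0.08 and 0.16, n=5 per group, printed effect size 2.68, printed power 94%. Assumed, because the documents do not say: two-sided alpha 0.05; rho; the sham-session SD; and an equal mean sham response in the two groups, so that the difference stays at 0.34.

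**Step 1: reproduce the printed figure.**
- Effect size: 0.34 / sqrt((0.08² + 0.16²)/2) = 0.34/0.1265 = 2.69 (printed 2.68). No sham-rTMS session enters.
- Noncentrality: 0.34 / sqrt(0.08²/5 + 0.16²/5) = 0.34/0.08 = 4.25.
- Noncentral t power: 93.8% with unequal variances (5.9 df) and 95.9% pooled (8 df). One-sided 0.05 would give 98.0% to 98.7%, so two-sided 0.05 is the better match.

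**Step 2: move to the difference score.** Its variance within a group is SD_active² + SD_sham² − 2·rho·SD_active·SD_sham. If the two SDs are equal, the SD is the single-session SD times sqrt(2(1 − rho)). At rho=0 the factor is 1.414, giving SDs of 0.113 and 0.226. At rho=0.5 the factor is 1.

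Power, unequal-variance to pooled, at three alpha levels:

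| rho | 0.05 | 0.05/4 | 0.05/10 |
|---|---|---|---|
| 0 | 70.5% to 74.9% | 40% to 47% | 23% to 31% |
| 0.3 | 84% to 88% | 56% to 65% | 37% to 47% |
| 0.5 | 94% to 96% | 73% to 82% | 53% to 66% |
| 0.7 | over 99% | 93% to 97% | 80% to 90% |

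The adjusted columns are shown because the analysis section commits these contrasts to Bonferroni. It lists four contrasts plus six for the acute and lasting time periods, and does not state the divisor.

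**Step 3: vary the sham SD.** Sham/sham is the same condition in both groups, so one common sham SD is at least as natural an assumption. At two-sided 0.05:

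| Common sham SD | Power at rho=0 (unequal-variance to pooled) | Printed 94% reached at rho of about |
|---|---|---|
| 0.08 | 86% to 88% | 0.25 to 0.3 |
| 0.12 | 76% to 77% | 0.45 |
| 0.16 | 63% to 64% | just above 0.6 |

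The break-even correlation therefore depends on an SD that the documents do not give. When the sham SD is a fixed multiple of the active SD in each group, the printed figure is too high exactly when rho < SD_sham/(2·SD_active).

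**Step 4: contrasts 1 and 2.** For the acute 1 Hz tDCS contrast (0.89 versus 0.64, SD 0.08), the unpaired test gives 99.0%. A paired test with 4 df gives 95.1% at rho=0, 98.5% at 0.25 and 99.9% at 0.5. The unpaired figure is conservative there once rho is moderate or high.

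**The case against.** The strongest reply is that the protocol does bear on rho. The section on TMS/EEG as an assessment tool describes TEPs as highly repeatable from test to test, especially with stereotaxic targeting, and the targeting section commits to marking every site for that purpose. That points to the region where 94% is about right or even too low. It stands as evidence that rho=0 is a worst case. It does not settle the value: no number is given, and repeatability of a TEP is not the correlation between values after sham and after active rTMS. The Scientific Premise section itself says that individual responses to rTMS vary, and that variation enters only the active session.

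A second reply is that the section is candid. It says that TEP data for a power analysis do not exist, that collecting them is one purpose of the pilot, and that the inputs are MEP amplitudes with 5 Hz standing in for 10 Hz. It also prints 8% for the same contrast at 30 minutes. No decision rule depends on the 94%. This limits the consequence but does not support calling the figure conservative.

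A reader might infer that the 94% overstates power by about 20 points. The documents do not support that as a general statement. It needs rho near 0 with the sham SD equal to the active SD in each group; with equal SDs the loss vanishes at rho=0.5 and reverses above it. Nor is 94% an arithmetic slip, since it reproduces.

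**Conclusion.** The point holds as a mismatch and an unsupported description, not as a demonstrated overstatement. The printed 94% describes a comparison of single-condition amplitudes, while the plan compares difference scores. For contrasts 3 and 4 nothing in the calculation makes it conservative.

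At two-sided 0.05 with equal SDs, planned-outcome power runs from 70.5% to 74.9% at rho=0, through 94% to 96% at rho=0.5, to over 99% at rho=0.7. Both the direction and the size of the error rest on rho and the sham SD, which the documents do not give. A reader might also infer that the design reaches 94% only if sessions correlate at 0.5 or more. That threshold belongs to the equal-SD assumption and moves from about 0.3 to above 0.6 as a common sham SD goes from 0.08 to 0.16.

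The Bonferroni adjustment, which is not reflected in the 94%, lowers power at any rho: with equal SDs at rho=0.5, 0.05/4 leaves 73% to 82%.

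**What to change.** In Power Estimates:

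1. Limit the word conservatively to the sham versus active tDCS contrasts (1 and 2), where it holds if a subject's sessions are at least moderately correlated.
2. State that the 94% applies to single-condition MEP amplitudes at unadjusted two-sided 0.05, if that is the alpha used.
3. Restate power for the frequency contrasts on the planned difference score, as a range over stated values of rho and the sham-session SD, at the Bonferroni-adjusted alpha and with the divisor named. For example, with equal SDs at 0.05/4: about 40% to 47% at rho=0, 73% to 82% at rho=0.5 and 93% to 97% at rho=0.7.

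The cost is a few sentences and a less favourable stated figure. No design change, new data or additional subjects are needed.

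### The stated powers for Aims 1 and 2 fit an unadjusted level near 0.05, not the planned Bonferroni level; one power does not match its effect size, one contrast has no power, and sufficiency does not follow

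*Combined protocol and SAP*

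**What the plan says.** Under Data Analysis (Analyses and Power calculations), Aims 1 and 2 share one analysis with four contrasts of interest:

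1. sham versus active tDCS at 1 Hz;
2. sham versus active tDCS at 10 Hz;
3. 1 Hz versus 10 Hz after sham tDCS;
4. 1 Hz versus 10 Hz after active tDCS.

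The text continues: "An additional 6 contrasts will be used to examine differences in the means" (for the acute and lasting periods). The hierarchical model is to give estimates "for all these contrasts of interest with a Bonferroni comparison procedure to adjust for the multiple contrasts". No overall alpha and no divisor is given.

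Under Power Estimates, the method is: "PASS 12 was used to calculate power by estimating power, conservatively, as two-sample t-tests (n=5 for all comparisons". The inputs are published motor-evoked-potential (MEP) results, and "power estimates for 10 Hz stimulation were based on the 5 Hz study". Six powers are printed, for contrasts 1, 2 and 4 at the acute and 30-minute times. There is no alpha, no mention of an adjustment and no figure for contrast 3. The section says: "One purpose of the pilot study is to collect TEP data for a power analysis because such data does not currently exist". It ends: "These estimates give confidence that the sample sizes of our pilot study are sufficient to test Aims 1 & 2". The Subject flow paragraph makes a similar claim of sufficiency and refers the reader to the analysis section.

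**The concern.** Power has to be computed at the level the analysis will use. If the planned test is Bonferroni-adjusted and the power is not, the justification describes a more lenient test than the one to be run. With 5 per group the loss is large.

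The printed figures also raise doubts of their own. One power does not match the effect size beside it, and one of the four main contrasts has no figure. Half of the printed powers are below 50%, yet the conclusion is favourable without saying which contrasts it covers. A reader could take a null result on a weakly powered contrast as informative.

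**Working it through.** **Inputs (Power Estimates section).** Two-sample t-test, 5 per group, 8 df. Acute MEP means (SD): 1 Hz sham .89 (.08), 1 Hz active .64 (.08), 5 Hz sham .99 (.16), 5 Hz active .98 (.16). Printed effect sizes d: 2.95, .95 (printed as 95%), .06, 4.80, 2.68, .39.

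**Assumption.** Overall two-sided alpha of 0.05. Bonferroni levels: 0.05/4 = 0.0125; 0.05/10 = 0.005 (four plus six contrasts, the natural reading); 0.05/20 = 0.0025 (if temporal and frontal sites count separately).

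**Formula.** Noncentrality δ = d × √(5/2) = 1.581 d. Power = P(|T| > c), where T is noncentral t with 8 df and c is the two-sided critical value: 2.306, 3.206, 3.833 and 4.334 at the four levels.

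**Step 1: effect sizes from the printed means.**
- Contrast 1 acute: (.89 − .64)/.08 = 3.125 (printed 2.95; both are used below).
- Contrast 2 acute: .01/.16 = 0.0625 (printed .06).
- Contrast 4 acute: pooled SD = √((.08² + .16²)/2) = .1265; .34/.1265 = 2.69 (printed 2.68).
- Contrast 3 acute (not printed): (.99 − .89)/.1265 = 0.79.

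**Step 2: power.** Where SDs differ, ranges run from Welch (1,000,000 simulated trials) to pooled.

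| Contrast, time | d | Stated | 0.05 | 0.0125 | 0.005 | 0.0025 |
|---|---|---|---|---|---|---|
| 1 acute | 2.95–3.125 | 99% | 98–99% | 89–92% | 76–81% | 63–70% |
| 1, 30 min | .95 | 48% | 26% | 10% | 5% | 3% |
| 1, 30 min | 1.37 | 48% | 48% | 23% | 13% | 8% |
| 2 acute | .06 | 6% | 5.1% | 1.3% | 0.5% | 0.3% |
| 2, 30 min | 4.80 | 100% | 100% | >99.9% | 99.7% | 98.8% |
| 4 acute | 2.68 | 94% | 93–96% | 70–81% | 52–65% | 39–52% |
| 4, 30 min | .39 | 8% | 8.5% | 2.5% | 1.1% | 0.6% |
| 3 acute | 0.79 | none | 18–20% | 6–7% | 3% | 2% |

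Smallest d with 80% power: 2.02, 2.64, 3.08 and 3.43 at the four levels.

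**Step 3: which level was used.** At 0.05, five of the six stated powers reproduce within 2 points. Power at a near-zero effect is close to alpha, so the statement that power "was only 6% acutely (effect size=.06") is the clearest marker: it would be 1.3% at 0.0125 and 0.5% at 0.005. The 8% at d = .39 points the same way. The 100% at d = 4.80 cannot separate the levels.

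**Step 4: the pair that fails.** The text gives "48% at 30 minutes (effect size=95", the last number carrying a percent sign. Read as d = .95, δ = 1.502 and power is 26.3%. A power of 48% needs d of about 1.37. With d = .95, a one-sided 0.05 test gives 39%; 48% in a two-sided test would need an alpha of about 0.145. The 30-minute means and SDs are not printed, so the documents do not show which figure is wrong.

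**Step 5: the two-sample approximation.** Contrasts 1 and 2 are within-subject. For contrast 1 acute (d = 2.95) at 0.005:

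| Test | Correlation 0 | Correlation 0.5 |
|---|---|---|
| Paired t, 4 df | 41% | 74% |
| Same, 8 error df | 76% | 98% |

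The two-sample figure is 76%. The approximation can therefore be too high or too low, depending on a correlation and error df that the plan does not give.

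**The case against.** The strongest reply is that this is a pilot that says so. Collecting data for a later power calculation is a stated purpose, the low powers are printed openly, the MEP source and the 5 Hz proxy are disclosed, and the Subject flow paragraph refers to the full figures. Each contrast that is given a power reaches at least 94% at one of its two times, which may be what the authors meant by sufficient.

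The level is also inferred. No single alpha reproduces every rounded figure exactly, so the safe statement is near 0.05 and not a Bonferroni level. The divisor is open too: at 0.0125 contrast 1 acute keeps 89–92%, and counting the two sites separately is the more speculative reading. Contrast 3 is not the direct test of the working hypothesis, and its d of 0.79 combines means from two separate studies.

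These points limit the weight of the finding but do not remove it. None of the Bonferroni levels considered fits the printed 6% and 8%. The one-time-point reading of sufficient is not stated, and it weakens after adjustment: at 0.0125 contrast 4 acute is 70–81%. Within-subject pairing cannot be counted on to offset the adjustment, and contrasts 3 and 4 compare parallel groups, so they gain nothing from it. The mismatched pair and the missing contrast are unaffected by these arguments.

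**Conclusion.** The concern holds. The stated powers belong to an unadjusted two-sided level near 0.05, while the plan tests at a Bonferroni level. Under the plan's own two-sample approximation with ten contrasts, contrast 2 at 30 minutes alone clearly exceeds 80%; contrast 1 acute is borderline and contrast 4 acute falls short. The 48% and .95 cannot both be right under the stated test, and contrast 3 lacks a figure. The sufficiency statements do not follow even without adjustment.

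This rests on an assumed overall two-sided alpha of 0.05, an unstated divisor and MEP-based effect sizes, so the recomputed powers are approximate. The design and analysis are not invalidated; what needs correcting is the level used for power and the conclusion drawn from it.

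**What to change.** 1. Restate the powers at the Bonferroni level to be used in the analysis, naming alpha and the number of contrasts (10, or 20 if the two sites count separately).
2. Check the 48% and its effect size against the source study and correct whichever is wrong.
3. Add contrast 3.
4. Keep the existing disclosure of MEP inputs and the 5 Hz proxy. Replace the description of the two-sample test as conservative with a statement that it may be too high or too low for contrasts 1 and 2.
5. Replace the sufficiency claims in Subject flow and Power Estimates with wording such as: *At the Bonferroni level of [x], 5 per group gives 80% power for standardized differences of about [2.64 at 0.0125; 3.08 at 0.005; 3.43 at 0.0025] or larger. On MEP-based estimates this is met for [contrasts and times]. All contrasts remain in the adjusted analysis; those with low power will be described as estimates for planning.*

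The cost is one recomputed table and some wording. No subjects, visits or contrasts change. The drawback is that the figures become less favourable.
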